## 1.0 PROJECT SUMMARY

Chronic obstructive pulmonary disease (COPD) is an incurable and progressive lung disease associated with poor quality of life (1). At The Ottawa Hospital (TOH), 20% of patients with COPD are readmitted to hospital within 30-days after discharge, and COPD is responsible for the highest 30-day readmission rate to the emergency room in Ontario when compared to other chronic diseases (2).

Integrated COPD care programs (ICPs) are promising interventions that have been shown to improve quality of life and readmission rates in the COPD patient population (3). ICPs are disease management programs which aim to systematically reduce fragmented patient care; a central problem in today's health system. ICPs often include patient education, self-management, access to a case manager, and care interventions that address the psychological and rehabilitative aspects of the disease (e.g. pulmonary rehabilitation) (4). Studies of integrated care program effectiveness have yielded conflicting results with respect to clinical outcomes. The interventions within the care programs are not often explicitly reported in a way that would allow for replication in other sites. Further, cost effectiveness of ICPs has not been well studied, and the most-appropriate target patient population which could benefit most from these care interventions has not been identified. Most ICPs were also designed as a 'one-size-fits-all' model, where all enrolled COPD patients would receive similar care. Lastly, patient reported outcome data in these studies is notably absent. (4,5).

To address these stated shortcomings, we developed a unique goal-directed COPD care program which streamlines most appropriate care and health resources based on the degree of frailty of a patient. This care model begins at the onset of a hospitalization and integrates ongoing disease management services and programs in the community after hospital discharge. Using this goal-directed frailty-based integrated system of care, we aim to improve the confidence of patients to cope with health challenges, improve health system outcomes, and reduce costs of care. In this preliminary study, we will determine whether it is feasible to implement our goal-directed, frailty-based COPD care pathway in a large hospital setting. We will also evaluate our ability to measure patient reported and important health service outcomes.

## 2.0 BACKGROUND

COPD is an incurable and debilitating lung disease that causes progressive breathlessness, disability, poor quality of life, and premature death (1). COPD is characterized by progressive airflow obstruction and recurring 'flare-up's' (also known as exacerbations) that often require patients to seek medical attention in an emergency department (1). Most cases of COPD are caused by long-term tobacco use and exposure to biomass fuels (1).

COPD affects over 300 million people worldwide and accounts for 5% of global deaths (10). It is the only chronic disease in which the mortality rate is still rising (11,12). COPD is also a leading cause for hospital admission and the number one reason for hospital readmissions among chronic illnesses in Canada (13).

COPD is estimated to exceed 700 million dollars annually to the Canadian health system (14). The majority of this cost is related to the hospitalizations and readmissions of COPD patients (14). The highest in-hospital costs are borne by patients with COPD who are frail and those with increased physical care needs (15,16).

A recent evidence synthesis performed by Health Quality Ontario (HQO) aimed to answer important questions relating to patient and caregiver experiences over the course of illness for patients with COPD (17). The authors reviewed and summarized a decade worth of qualitative evidence to understand the daily life experiences of patients with COPD. The resulting information offers valuable insights on the types of interventions that could have a substantial impact on the experiences of patients with COPD (17).

Below is a summary of several important themes identified by HQO in their knowledge synthesis of patients' experiences with COPD.

- Patients may not realize that COPD is incurable and fatal; some physicians themselves do not consider early COPD to be a fatal disease.
- Patients may not attribute repeated exacerbations to advancing disease, seeing them as temporary setbacks instead.
- Economic hardship, co-morbidities, language barriers, low health literacy can make coping difficult.
- Many factors that isolate COPD patients from social contact also isolate them from health care professionals (or seeking out health care).
- Lack of confidence in community -based services leads some patients to seek hospital admission, but patients also feel vulnerable when hospitalized.
- Patients feel dependent on others for care or traumatized by hospital care routines
- Upon discharge following an exacerbation, patients may face new levels of uncertainty about their illness, prognosis, care providers, and supports.
- Patients tend to be poorly informed about the long-term prognosis of COPD, and what to expect toward the end of life; lack of understanding impairs quality of life as disease progresses.
- A palliative care referral can convey the demoralizing message that care providers have “given up”.

These valuable insights from patients and their caregivers underscore the need for improved disease-specific education, the nature of symptoms and prognosis, re-enforcement around the use of pharmacologic and non-pharmacologic treatments over time, and readily available access to a health care professional who could connect the patient to the most appropriate health services.

Studies have demonstrated that Integrated COPD care models are associated with reduced readmission rates and improved quality of life in single center studies (3, 4, 19). However, studies of integrated care models make it difficult to discern which aspect of the care programs can be replicated and scaled in other sites and settings. It is also unclear which COPD patients derive most benefit from these programs, what effect there is on patient reported outcomes, and what resources are required to effectively run and scale these programs. As a result, the American Thoracic Society (ATS) has highlighted the need for further studies to evaluate components of care models on patient centered outcomes and to better define sub-types of COPD patients who might benefit from integrative care models (4).

Previous care models have used a 'one-size-fits-all' approach to care, in which all-comers with COPD are offered the same set of interventions and treatment. However, all COPD patients are not alike. Simply classifying patients by their lung function or age does not correlate with symptoms or outcomes (20). Patients with COPD are often managing multiple comorbidities, mental health conditions, addictions, and social factors that contribute to their overall health care utilization. These factors underscore the need to have a more personalized and multidisciplinary care-delivery approach in this patient population.

Based on our knowledge of existing integrated care programs, we developed a unique integrated care program specifically for COPD patients. This care model begins in the hospital setting when a patient is admitted with an acute COPD exacerbation. Evidence based care including disease-specific education is provided and a safe transition after discharge is planned by integrating the patient with a variety of community services (education, rehabilitation, home care, disease-specific outreach, etc.). Continuity of care for the patient is provided through healthcare providers who straddle both the community and hospital settings.

Our integrated care model is unique as it groups hospitalized patients with COPD into functional health states using a validated clinical frailty indicator (8). Specific health goals are correlated with each health state and recommendations are made to involve various care providers to meet these goals (see Appendix B).

The following are additional unique features of the proposed care model:

- The care model is organized into 3 phases of hospital care relevant to the rescue, optimization, and safe transition.
- Hospital care delivery will be integrated with community care delivery through the pre-existing COPD Outreach program for frail individuals with most severe disease (i.e. those most likely to benefit from close follow up and management). The outreach program consists of follow up phone calls at 3 and 12 months, a home visit, ongoing education, and a hotline that patients may call if they have concerns. Individuals with less severe disease will be linked to existing COPD education and maintenance pulmonary rehabilitation programs in the community to ensure ongoing support and follow up.
- The care model also incorporates testing to confirm the COPD diagnosis and reinforces the importance of performing spirometry to confirm the diagnosis. This is a 'real world' issue, as many patients presenting to hospital with "COPD" have never actually been formally diagnosed (20). Confirmation of diagnosis offers an opportunity to intervene with treatments to improve quality of life in the long term.

We will use a patient reported outcome measure engagement called 'Health Confidence' as an outcome for this care model. Health confidence has not traditionally been a patient reported outcome in COPD, but patients consistently indicate it to be an important issue (17). Improving the health confidence of patients can contribute to improved health outcomes, better care experiences, and likely fewer health care services with less cost (27).

### **3.0 OBJECTIVES**

The objectives of this study are to:

- a) Determine the feasibility of implementing a novel COPD care model on a respiratory ward in a tertiary care hospital using *quantitative* and *qualitative* implementation metrics.
- b) Determine the process measures and personnel required for successful replication of this care model intervention at other sites.
- c) Use the results of this pilot feasibility study to determine the optimal study design and plan for a larger scale analysis to study the effect of this care model on health system and patient-reported outcomes.

### **4.0 HYPOTHESIS**

We hypothesize that goal-directed care delivery which is tailored to the functional health status of patients will improve patient engagement (health confidence) and translate into improved health service and clinical

outcomes in the short and long term. To rigorously test this hypothesis, we must first demonstrate feasibility of this complex intervention.

## 6.0 METHODS

**6.1 Design:** a prospective, mixed-methods, cohort study design at The Ottawa Hospital (TOH) to evaluate feasibility of this complex intervention.

**6.2 Study population and Inclusion Criteria:** We will include adult patients admitted to the 6NW (Respirology ward) of the General campus at TOH with a primary diagnosis of acute exacerbation of COPD (AECOPD). The diagnosis is based on the admitting physician's assessment of the patient in the emergency room.

We will also include approximately 26 health care workers (nurses, physicians, and allied health professionals) who care for patients on the 6NW of the General campus at TOH who have implemented and worked with the COPD care pathway during the study duration.

**6.3 Time Frame:** Implementation and feasibility data will be collected for 50 patients who are hospitalized for COPD over the course of two flu seasons (2017-2018 and 2018-2019), which corresponds to the peak season for COPD-related hospitalizations (22).

**6.4 Consent Process:** Patients eligible for the study will be approached by the study respiratory nurse educator (RT), who is already part of the patients circle of care. The RT will ensure the potential participant understands the study and what it would require of them (two questionnaires: one in hospital and one during a 3-month post-discharge visit). If the patient accepts, the RT will ask them to review the Informed Consent Form and sign if they agree to participate in the study.

A member of the study team will approach Healthcare professionals (HCPs) who work on the Respiratory ward (6NW) of TOH, General campus and have used the COPD care pathway to participate in the study. The member of the study team will explain the study and ask if they would

like to participate. If they agree to participate, they will be given a consent form. The consent form requests a consent to complete a questionnaire and participate in the focus group with other HCPs. If the HCP chooses to participate, the signed informed consent is placed in one box, while the completed questionnaire is placed in another. This is to conserve anonymity of the questionnaire responses. Once focus group times and location are set, an email will be sent out by a member of the study team to inform those who consented to participate of the focus group time and location.

**6.5 Implementation of the Goal-Directed Care Pathway:** Patients enrolled in the study will receive standardized treatment using an initial physician order set followed by a clinical care pathway (Appendix B). The order set and care pathway will be physically added to the patient's chart for daily reference by the health care team.

The care pathway (see Appendix B) consists of orders to be executed by the nursing staff, attending physician, and allied health professionals (respiratory therapy, occupational therapy, and physiotherapy, where applicable) while the patient is hospitalized. None of the components of the pathway extend beyond standard care that would be provided at TOH.

To initiate the care pathway, the first nurse to admit the patient will complete a frailty assessment and document the patient's clinical frailty score (8). This validated frailty score is associated with a set of expected treatment goals and outcomes for the patient during hospitalization and will serve to guide the subsequent care for the patient.

Following the frailty assessment, the care pathway is divided into three phases: rescue, optimization, and safe transition. The interventions in each phase are tailored to the COPD patient based upon their frailty rating. Evidence-based pharmacologic treatments, consultations with allied health professionals, medical services (e.g. Palliative care), and multidisciplinary educational interventions (Appendix A) are ordered in each phase where appropriate. In the safe transition phase, follow up with primary care, and referrals to pulmonary rehabilitation and the COPD outreach program will be arranged where appropriate.

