## 6.6 Sample Size:

**6.6.1 Patients:** We aim to recruit 50 unique patients over an 18-month period to use the care pathway. The Ottawa Hospital admits over 500 patients with acute exacerbations

of COPD annually and approximately 30% of these patients are admitted to the respiratory inpatient service (150 patients). Given that COPD exacerbations are twice as common in the winter months (22), we feel our recruitment target of 50 patients is feasible between November 2017 and May 2019.

**6.6.2 Health Care Professionals (HCPs):** We aim to recruit approximately 26 HCPs, 2 groups of 13 participants, to discuss of their personal experiences with the COPD care Pathway after an evaluation of the pathway.

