## 6.7 Outcomes

**6.7.1 Primary: The primary outcome is the feasibility of using this COPD care model in a hospital setting.** In this practical experiment, feasibility will be defined by recruitment of 50 patients (3-4 per month x 18 months) to the care pathway, with an 85% completion rate (care model completion). This will be calculated using the number of completed pathway documents divided by the total number of care pathways initiated at the time of admission. We will critically review each document for completion.

**6.7.2 Secondary:** There are four secondary outcomes for this study.

**6.7.2.1 Qualitative Implementation Metrics:** Implementation of the care pathway will be evaluated by HCPs (nursing staff and allied health professionals). Participants are asked to complete a questionnaire and participate in a focus group with other HCPs. During focus groups, common themes for barriers to implementation will be identified using a-priori selected questions. We will consider success of implementation if no significant barriers are identified through group consensus in the focus groups and if 80% of questionnaire responses in each category fall into the “agree” or “strongly agree” responses.

**6.7.2.2 Knowledge Translation Metrics:** We will measure success in knowledge translation with achievement of 80% adherence to basic COPD care guideline standards including use of appropriate antibiotics, systemic steroids, bronchodilators, venous thromboembolism prophylaxis, and advanced directives documentation. Adherence will be calculated from direct review of the care pathway documents after completion.

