## 6.8 Data Sources:

- 6.8.1 **Electronic Health Record, COPD Pathway Documents:** We will collect patient-related data using and some feasibility data using a combination of vOacis and the COPD care model document. These data points are detailed in the case report forms.
- 6.8.2 **Focus Groups and Questionnaires:** We will gather data from focus groups of HCPs to assess our implementation outcomes, and questionnaires provided to the HCPs who use the care models.
- 6.8.3 **Patient Questionnaires:** We will gather data from the COPD Assessment Test (CAT) and Health Confidence scores (HCS) to assess the symptom burden and engagement of patients.
- 6.8.4 **TOH Data Warehouse (TOHDW):** Health service metrics including length of stay, cost per weighted case, readmissions, mortality, and ICU admissions will be ascertained from the Data Warehouse. A separate Data Specification Form (DSF) has been initiated for this data request.

**6.9 Data Collection:** The following figure illustrates when data will be collected for participant during the study. The two focus groups will be conducted during the pilot in March 2018 with HCPs (nurses, physiotherapists, occupational therapists, and dieticians) who have used the pathway. Questionnaires of HCPs will be gathered prior focus groups.

Patient data will be collected at three time-points:

- 1) **During hospitalization:** Includes COPD Pathway Phases 1 to 3. Patient data relating to demographics, frailty rating, COPD diagnosis, lung function, oxygen use, smoking status,

and symptom burden will be collected from the hospital chart. The study respiratory therapist will enter this data in a Case Report Form for Respiratory Therapists. Patient participants are asked to complete a baseline health confidence and quality of life questionnaire at the beginning of hospitalization (Part A – Patient In-Hospital Questionnaire).

- 2) **3-Months Post-Discharge:** Includes COPD Pathway Phase 4. During a post-discharge visit in the PFT laboratory of the General Campus at TOH, patient participants will be asked to complete a follow up questionnaire (Part B – Patient Post-Discharge Questionnaire). During this visit, a review will be undertaken of community services accessed by the patients, and any referral issues will be rectified if needed.

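### Only staff who have used the pathway are asked to judge it, and only a joint consent to questionnaire and focus group is described, so reasons for non-use can be missed and the implementation verdict may lean toward success

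*Protocol*

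**What the plan says.** The limit to users appears in four places in the protocol.

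- Section 6.2 includes about 26 ward professionals "who have implemented and worked with the COPD care pathway during the study duration".
- Section 6.4 approaches those who work on 6NW "and have used the COPD care pathway to participate in the study".
- Section 6.8.2 sends the questionnaires to users of the care model.
- Section 6.9 holds the focus groups "with HCPs (nurses, physiotherapists, occupational therapists, and dieticians) who have used the pathway".

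On consent, section 6.4 states: "The consent form requests a consent to complete a questionnaire and participate in the focus group with other HCPs". Signed forms and completed questionnaires go into separate boxes so that answers stay anonymous. No route to the questionnaire alone is described.

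Section 6.6.2 gives the size: "We aim to recruit approximately 26 HCPs, 2 groups of 13 participants". Section 6.7.2.1 gives the rule in two parts. The first is: "We will consider success of implementation if no significant barriers are identified through group consensus in the focus groups". The second sets an 80% threshold for favourable answers (agreement or strong agreement), to be met in every questionnaire category.

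**The concern.** The rule in 6.7.2.1 is a verdict on barriers to implementation. A barrier strong enough to stop someone using the pathway also takes that person out of the sample. Nobody in the sample is there to report why the pathway was left unused, and the protocol text does not provide for recording how much each respondent used it. The joint consent may add a second filter, since a person reluctant to speak in front of colleagues is offered only the combined package.

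If the people left out are less favourable, both parts of the rule become easier to meet. The result feeds objective (a), feasibility of implementation, and objective (b), what other sites need for replication. It would also inform the cluster randomized trial named in section 7.0, where non-adoption would matter directly.

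**Working it through.** **1. The plan's own figure.** 2 groups × 13 = 26, which agrees with section 6.6.2. There is no power calculation behind it and none is disputed here. The point concerns who is sampled.

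**2. Does another part of the protocol capture non-use?**

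- The primary completion rate (6.7.1) divides by pathways started at admission, so a pathway never started is not counted.
- Guideline adherence (6.7.2.2) is read from pathway documents after completion.
- The pathway forms in Appendix B carry a code for patients ordered off the pathway. That records the event for a patient, not staff views.
- The monthly trainee focus groups and the pre-implementation improvement cycles (7.0) are not tied to the 6.7.2.1 rule.
- Figure 1 and section 7.0 mention ward staff without repeating the limit to users, but they do not widen the eligibility set in 6.2.

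So no part of the success rule draws on staff who did not use the pathway.

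**3. How far could the 80% part move?** The protocol gives no non-user share and no agreement rates, so every rate below is an assumption. Take one category as one independent response from each of 26 staff. Then 0.80 × 26 = 20.8, so at least 21 must agree (21/26 = 81%). Let *s* be the share of staff outside the present sample, *p_u* the agreement among users and *p_n* the agreement among the rest.

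- All-staff agreement: *p* = (1 − *s*)·*p_u* + *s*·*p_n*
- Chance of passing: P(X ≥ 21), X ~ Binomial(26, *p*)
- Share at which true agreement reaches 80%: *s** = (*p_u* − 0.80)/(*p_u* − *p_n*)

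| *p_u* | *p_n* | users only | *s* = 10% | *s* = 20% | *s* = 30% | *s** |
|---|---|---|---|---|---|---|
| 85% | 50% | 0.82 | 0.65 | 0.48 | 0.32 | 0.05/0.35 = 14% |
| 85% | 30% | 0.82 | 0.55 | 0.30 | 0.13 | 0.05/0.55 = 9% |
| 90% | 50% | 0.96 | 0.85 | 0.68 | 0.48 | 0.10/0.40 = 25% |
| 90% | 30% | 0.96 | 0.77 | 0.48 | 0.22 | 0.10/0.60 = 17% |

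If *p_n* = *p_u*, then *p* = *p_u* for any *s* and there is no bias.

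**4. The same point in head counts, in both directions.**

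- Start from 22/26 = 85%, a pass. Adding 10 at 40% gives (22 + 4)/36 = 72%. Adding 14 at 40% gives (22 + 5.6)/40 = 69%. Adding 14 at 60% gives (22 + 8.4)/40 = 76%. All three fail.
- Start from 24/26 = 92%. Adding 10 at 60% gives (24 + 6)/36 = 83%. Adding 14 at 60% gives (24 + 8.4)/40 = 81%. Both still pass.

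Whether the verdict changes therefore depends on inputs that the protocol does not supply.

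**The case against.** The strongest reply is that the excluded group may hardly exist. Section 6.5 puts the order set and pathway in the enrolled patient's chart and expects nurses, physicians and allied health staff to carry them out. The Appendix B forms ask for a sign-off on each shift. Nurses looking after an enrolled patient are thus users largely by design. The wording in 6.4 and 6.9 sets no minimum of use, so occasional users can qualify. This stands, and it limits the likely size. It does not remove the gap, because a form in a chart does not prove use and the protocol makes use a condition for approaching staff.

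A reader might infer that anyone who declines the focus group is barred from the questionnaire. The protocol does not say so. It describes one joint consent and no alternative, and the consent form itself is not available to check. A reader might also infer that non-users know the barriers best, or that those who decline a focus group are the critics. The documents support neither, and users meet barriers too.

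Asking users about their experience is also a coherent aim, and section 6.6.2 states it. Items about experience of use cannot be answered validly by non-users. That stands and shapes the fix.

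Finally, inviting all staff who saw any eligible patient would go too far. Only enrolled patients receive the pathway, and the focus groups fall in March 2018, about four months after recruitment opens in November 2017. Some staff would never have had the chance to use it, and pooling them into the 80% rule would confuse non-exposure with avoidance.

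**Conclusion.** The point holds in a limited form. The user-only sample is explicit in four sections, it alone decides the 6.7.2.1 verdict, and nothing else in that rule repairs it. If non-users, or staff put off by the joint consent, are less favourable, the verdict leans toward success. If they are not, there is no bias.

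The size cannot be computed from the protocol. In the assumed scenarios, true all-staff agreement falls below 80% once the missing share exceeds 9% to 25%. With few complete non-users the effect would be small. A reader might infer that the feasibility conclusion as a whole is biased. The documents do not support that: this is one secondary outcome, the primary verdict rests on recruitment and 85% completion, and the implementation rule requires both of its parts to be met. The change is worth making because it is cheap.

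**What to change.** - **Eligibility (6.2, 6.4, 6.8.2, 6.9).** Invite all 6NW professionals who cared for at least one enrolled patient, whatever their level of use. This includes staff who had the chance to use the pathway and leaves out those who never met it.
- **Questionnaire.** Add one item on use (used, seldom used, not used) with the reason for non-use. Items that rate experience of use stay with users.
- **Consent (6.4).** State that the anonymous questionnaire may be returned without joining a focus group.
- **Reporting and rule (6.7.2.1).** Report the number invited, the response rate, and agreement overall and by level of use. Count reasons for non-use when judging whether "no significant barriers are identified through group consensus in the focus groups".

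The cost is revised wording in five sections, a revised consent form and one extra questionnaire item. The agreement figure may be less favourable.
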